5.2. Efficacy study endpoints

Primary endpoint

The primary efficacy objective is to compare leprosy incidence rate. The health worker will perform a physical examination to look for signs of leprosy. Note that for this study, the diagnosis of leprosy will be made based on the so-called cardinal signs, i.e. a patch with loss of sensation, enlarged peripheral nerves and/or a slit skin smear positive for

acid fact bacilli. Results of qPCR and anti-PGLI testing will be not be used as diagnostic criteria.

Secondary endpoints

Genotyping will be done by a novel sequencing technique called the Deeplex® MycLep assay.

Rifampicin resistance will be tested with molecular markers.

6. Interim analysis

Two interim analyses will be conducted upon completing the second and third door-to-door surveys in which leprosy incidence rates to date in study arms 2, 3 and 4 will be compared to the leprosy incidence rate in arm 1, just as in the final analysis. These interim analyses will allow us to assess whether the a priori assumptions on annual incidence made have been realistic or whether an extended study duration should be considered.

The analysis performed will be similar to the analysis of the main efficacy outcome (Section 7) but restricted to data up to the second resp. third survey. Hence the interim analysis after completing the second survey will only include data from the Comoros.

7. Analysis of main efficacy outcomes: incidence rate of leprosy

Each diagnosis of leprosy made after the survey in which the participant was enrolled will be counted as an incident case. Note that not only diagnoses made at the annual surveys but also diagnoses made in between the surveys will be counted. For each individual we will calculate the exact time at risk. For individuals residing in intervention villages (arms 2, 3 and 4) we will use the number of days from the median date of the first SDDR-PEP administration in the village until end of follow-up or until diagnosis of leprosy.

We will fit a random effects Poisson model with incident case (0/1) as dependent variable, study arm as explanatory variable, using the non-intervention group (arm 1) as baseline level, log(time at risk) as offset, and with 'island', 'block' (as described above, eight on Anjouan, four on Mohéli, four to six on Madagascar) and 'village' as nested random effects. As study outcome we will report incidence rate ratios between arm 1 and each of the other arms with 95% confidence interval, considering a p-value of < 0.017 as statistically significant to account for the fact that we make three comparisons.

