2.1. Study design

The PEOPLE study is a cluster randomized trial. There will be four door-to-door surveys of which the first one will allow us to calculate a baseline leprosy prevalence

per island. On the Comoros villages have been randomized after having been grouped by island into 'Blocks' of four in decreasing order of incidence over the period 2013-2017. Within each block villages were randomly and mutually exclusively allocated to the four study arms. For the study district in Madagascar reliable incidence estimates were not available. For that reason randomization for Madagascar is foreseen only for the end of the first study year, once the first screening round has been completed.

There will be four study arms to which villages on Madagascar and the Comoros islands Anjouan and Mohéli will be randomly allocated. These villages have been preselected based on reported leprosy incidence over the period 2013-2017. In all four study arms, annual door-to-door surveys will be conducted covering entire villages. All permanent residents will be invited for screening for leprosy. Leprosy patients (further referred to as 'index patients') detected will be offered free treatment according to the international and country guidelines. Depending on the study arm, contacts of leprosy patients will be offered PEP. In arm 1 no PEP will be provided, which is the current routine care on Madagascar and the Comoros. In arms 2, 3 and 4 a single dose of 20 mg per kg bodyweight of Rifampicin (hereafter called 'SDDR-PEP') will be offered to all eligible participants who have not received Rifampicin in the preceding 2-year period. In arm 2 only household contacts of an index patient will be provided with SDDR-PEP, which target group is considered the standard approach when PEP is provided for leprosy. In arms 3 and 4 SDDR-PEP will also be provided to neighbourhood contacts living within a radius of 100 meter of an index patient. In arm 3 all such contacts (including household contacts) will be provided SDDR-PEP, in arm 4 SDDR-PEP will be provided to all household contacts and to all those within the 100-meter perimeter testing positive to a serological screening test. If in arms 3 or 4 more than 50% (arm 3) or 75% (arm 4) of the population live within 100 meters of an index case, the entire village will in principle be eligible for PEP.

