5.1. Patient populations

Note that in Madagascar enrolment/randomization will only take place at the second survey. Hence for Madagascar only data from the second survey onwards will be used for the primary objective. For secondary objectives 2 and 3 data from the first survey will also be used.

We will analyse the efficacy data using Intention-to-Treat and Per-Protocol approaches, with Intention-to-Treat as primary approach.

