5.1.1. Intention to treat (ITT) analysis

In the Intention-to-Treat analysis, all participants will be analysed according to their randomized allocation, even in case they do not receive SDDR-PEP as allocated, show protocol violations prior to or during the study.

5.1.2. *Per protocol (PP) analysis*

In the per-protocol analysis only participants who receive SDDR-PEP as planned, have complete follow-up, and follow the protocol as planned are included.

In Table 1 the protocol violations are classified as minor and major where minor violations can be included in the PP analysis population and major violations are excluded.

Table 1: The protocol violations classified as minor or major violation

Protocol Violation	Major/Minor Violation	Comments
Inclusion criteria		
1. Living in one of the study villages	Major	
2. Ages 2 years and above (only applicable for those receiving SDDR-PEP)	Major	
3. Able and willing to provide informed consent for leprosy and tuberculosis screening, and SDDR-PEP administration	Major	
4. For leprosy index cases only: able and willing to provide informed consent for participation and sampling	Major	
Exclusion criteria (only applicable for those receiving SDDR-PEP)		
1. Signs of active leprosy	Major	
2. Signs of active pulmonary tuberculosis	Major	
3. Having received Rifampicin within the last 24 months	Major	
Treatment violations		
1. Missing SDDR-PEP	Major	
2. Not following the randomized intervention	Major	
Follow-up violations		
1. Incomplete follow-up	Minor	

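### In arms 2-4, cases are counted from enrolment but time at risk starts at the village PEP date, so the primary rate ratio is generally not 1 when PEP has no effect

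*SAP*

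**What the plan says.** Section 7 of the SAP sets two rules that begin at different times.

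- **Cases, all arms:** "Each diagnosis of leprosy made after the survey in which the participant was enrolled will be counted as an incident case". Detection is not limited to survey visits: "not only diagnoses made at the annual surveys but also diagnoses made in between the surveys will be counted".
- **Time at risk, arms 2, 3 and 4 only:** "we will use the number of days from the median date of the first SDDR-PEP administration in the village", up to diagnosis or the end of follow-up.

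The time at risk enters the primary random effects Poisson model through "log(time at risk) as offset", with arm 1 as the reference. No starting date is written for arm 1. It cannot be a PEP date, because Section 2.1 states "In arm 1 no PEP will be provided". Enrolment is the natural reading.

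Three other statements bear on the point. Section 2.1 ties PEP to the presence of leprosy patients: "Depending on the study arm, contacts of leprosy patients will be offered PEP". Section 5.1 shortens follow-up in one country: "for Madagascar only data from the second survey onwards will be used for the primary objective". Section 5.1.1 leaves nobody out of the primary analysis: "all participants will be analysed according to their randomized allocation".

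**The concern.** A rate is interpretable only if its cases arise in the person-time beneath them. Here the two windows differ, and only in the intervention arms. Four consequences follow.

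1. **PEP lag.** If the village PEP date falls after the enrolment survey, disease arising in the gap and found later is counted, but the gap is removed from the denominator. The rate in arms 2-4 goes up.
2. **Late enrolment.** A resident of arms 2-4 who enrols at a later survey is credited with time from the village PEP date, before he or she could be counted as a case. The rate goes down.
3. **Undefined offset.** A counted case diagnosed on or before the village date has zero or negative time at risk, so its logarithm does not exist.
4. **No start date.** An intervention village in which no PEP is given has no date from which to start, yet its residents belong in the intention-to-treat analysis.

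This is the primary effect estimate, and part of any difference from arm 1 could come from the definition of time at risk. Items 3 and 4 can arise only in arms 2-4. If they are left open, someone will have to drop, truncate or re-date cases in those arms after seeing the data.

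**Working it through.** The SAP gives no figure for this bias, so there is none to reproduce.

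**Inputs from the SAP.** Four annual surveys (Section 2.1) give about 36 months of follow-up on the Comoros. Madagascar, counted from the second survey (Section 5.1), has about 24 months. The first interim analysis uses Comoros data only (Section 6), about 12 months. The significance level is 0.017 per comparison (Section 7).

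**Assumptions.** The hazard is constant, PEP has no effect, and arm 1 is timed from enrolment. The PEP lag L is 1-4 months. Late enrolment on the Comoros is 5% at survey 2 plus 5% at survey 3, or 15% plus 10%. In Madagascar 5% or 15% join at survey 3.

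**Formula.** Let T be follow-up and d the average enrolment delay per person. In arms 2-4, cases arise over T − d but the credited time is T − L. In arm 1 both are T − d. Hence

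null IRR = (T − d)/(T − L).

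**Lag alone (d = 0):**

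| Lag (months) | Comoros, 36/(36 − L) | Madagascar, 24/(24 − L) | First interim, 12/(12 − L) |
|---|---|---|---|
| 1 | 1.029 | 1.043 | 1.091 |
| 2 | 1.059 | 1.091 | 1.200 |
| 3 | 1.091 | 1.143 | 1.333 |
| 4 | 1.125 | 1.200 | 1.500 |

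**Late enrolment alone, Comoros, in years.** With 5% + 5%, d = 0.05 × 1 + 0.05 × 2 = 0.15 and the IRR is 2.85/3 = 0.95. With 15% + 10%, d = 0.15 × 1 + 0.10 × 2 = 0.35 and the IRR is 2.65/3 = 0.88.

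**Both together:**

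| Lag (months) | Comoros 5% + 5%: 2.85/(3 − L/12) | Comoros 15% + 10%: 2.65/(3 − L/12) | Madagascar 5%: 1.95/(2 − L/12) | Madagascar 15%: 1.85/(2 − L/12) |
|---|---|---|---|---|
| 1 | 0.977 | 0.909 | 1.017 | 0.965 |
| 2 | 1.006 | 0.935 | 1.064 | 1.009 |
| 3 | 1.036 | 0.964 | 1.114 | 1.057 |
| 4 | 1.069 | 0.994 | 1.170 | 1.110 |

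**Simulation.** With all cases found at the next survey and lags of 1, 2 and 4 months on the Comoros, simulation gave 0.977, 1.006 and 1.070 (5% + 5%), and 0.907, 0.934 and 0.994 (15% + 10%). These agree with the formula.

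**Undefined offsets.** If 30% of cases are instead found at onset, between surveys, 0.7-3.2% of cases in arms 2-4 have non-positive time. Dropping them gives a combined Comoros range of 0.90-1.04. Dropping does not cure the mismatch: with detection only at surveys nothing is dropped, and a 3-month lag still gives 3/(3 − 0.25) = 1.09.

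**Effect on the test.** Take SE(log IRR) = √(2 × DE/D), with an assumed D = 100-200 cases per arm and design effect DE = 1-2. The SE then runs from √(2/200) = 0.10 to √(4/100) = 0.20. The two-sided probability of p < 0.017 under no effect is 0.018-0.022 at an IRR of 1.03, 0.023-0.044 at 1.07 and 0.030-0.076 at 0.91.

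**Effect on the estimate.** An assumed true IRR of 0.60 would be estimated between 0.60 × 0.91 = 0.55 and 0.60 × 1.07 = 0.64.

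**The case against.** The best counter-argument concedes the mismatch and disputes its weight.

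- **Late enrolment is inferred.** The reference to each participant's enrolment survey may only reflect that Madagascar enrols at survey 2. The assumed shares have no source. If arm 1 were timed from the village baseline survey, equal late enrolment across arms would cancel. This stands: every figure below 1 is conditional on rolling enrolment and on arm 1 being timed from enrolment. The lag bias remains under either reading of arm 1.
- **The lag works against PEP.** The excess rejections it causes point to apparent harm. Under the same assumptions, the chance of a false finding in favour of PEP is about 0.004-0.006 at an IRR of 1.03 and 0.001-0.003 at 1.07, below the nominal 0.0085 per tail. This stands for lag alone; the cost there is attenuation and lost power.
- **The lag may be short.** Half a month gives 36/35.5 = 1.014 on the Comoros and 24/23.5 = 1.021 in Madagascar. The Comoros supply 12 of the 16-18 blocks. With an SE of 0.10-0.20, the 95% confidence limits lie a factor of about 1.22-1.48 from the estimate, so a shift of a few per cent is well inside sampling error. This also stands. However, the lag need not reflect slow field work: if a village's first leprosy patient is found at survey 2, its first PEP comes about a year after enrolment. That patient, if enrolled at survey 1, is a counted case with non-positive time. The SAP does not show how often this would occur.
- **The interim figures carry little weight,** since Section 7.2 says that the interim analyses do not affect continuation. Agreed.
- **Villages without PEP may not exist,** because villages were preselected on reported incidence. Possible, but the plan should not depend on it.

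None of this reconciles the two rules.

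**Conclusion.** The concern holds and should be fixed before the analysis is run. The primary analysis uses a time origin in arms 2-4 that does not match its own case definition and has no counterpart in arm 1. The null IRR is 1 if there is neither lag nor late enrolment, or if the two happen to offset each other.

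The existence of the mismatch is certain from the text; its size is not. On the assumptions above, the final-analysis bias ranges from negligible to about 13% on the Comoros and 20% in Madagascar from lag alone, and may fall to 9% below 1 on the Comoros if enrolment is rolling. At short lags it is small against sampling error. The undefined offset and the missing start date do not depend on the average bias being large: they need a rule, and the SAP has none.

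**What to change.** In the primary intention-to-treat analysis, define time at risk identically in all four arms: from the individual's own enrolment-survey date to diagnosis or last seen, with cases counted over exactly that interval. The null IRR is then 1 at any lag and any share of late enrolment. Every counted case has positive time, and every village has an origin whether or not PEP was given there. The set of counted cases does not change; only the denominators do.

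Keep an analysis from the PEP date as a sensitivity analysis if it is wanted. In it, give arm 1 villages and intervention villages without PEP a start date matched within block, start nobody before his or her own enrolment, and restrict cases to the same window.

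The cost is a change of SAP wording and one derived variable. The short period before PEP is included in arms 2-4, which is consistent with intention to treat and dilutes the effect slightly. For example, with an assumed rate ratio of 0.60 after PEP and 1 before it, over 36 months, the expected IRR is (1 + 35 × 0.60)/36 = 0.61 for a 1-month lag and (4 + 32 × 0.60)/36 = 0.64 for a 4-month lag.

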Statistical Analysis Plan

Post Exposure Prophylaxis for Leprosy in the Comoros and Madagascar

PEOPLE

Date: 24 September 2020

Author: [name]
Biostatistician, Institute of Tropical Medicine, Antwerp, Belgium

Approved by: Coordinating Investigator
[name]

Date: 24 / 09 / 2020

Table of Contents

1. Introduction.....	2
2. Study design and objectives.....	2
2.1. Study design	2
2.2. Study objectives	3
3. Deviations from protocol	3
4. Description of study population.....	4
4.1. Patient accounting	4
4.2. Description of study population	4
5. Description of efficacy patient populations and outcomes	4
5.1. Patient populations	4
5.1.1. Intention to treat (ITT) analysis	4
5.1.2. Per protocol (PP) analysis.....	5
5.2. Efficacy study endpoints	5
6. Interim analysis.....	6
7. Analysis of main efficacy outcomes: incidence rate of leprosy	6
7.1. Subgroup analyses.....	6
7.2. Other aspects	6
a. Multiplicity	6

b. Missing data	7
8. Analysis of secondary efficacy objectives	7
8.1. To assess cost and feasibility of SDDR-PEP under program conditions	7
8.2. To identify patterns of clustering in transmission of leprosy, allowing better targeting of control measures	7
8.3. To monitor rifampicin resistance among leprosy patients	8
9. Safety analyses	8
9.1. Safety analysis population	8
9.2. Safety outcomes and analyses	8
9.2.1. Adverse events	8

1. Introduction

This Statistical Analysis Plan (SAP) provides a detailed and comprehensive description of the main, pre-planned analyses for the study “Post Exposure Prophylaxis for Leprosy in the Comoros and Madagascar”, including interim analyses. The purpose of this study is to document effectiveness of three alternative ways of implementing post exposure prophylaxis (PEP) at village level, by comparing to villages in which no PEP is provided. The study conduct is described in the Protocol (Clinicaltrials.Gov. NCT03662022).

These planned analyses will be performed by the statistician(s) at the Clinical Trials Unit of the Institute of Tropical Medicine (Antwerp) and the research consortium. The analysis results will be described in a statistical analysis report, to be used as the basis of the primary research publications. This document describes statistical methods for the primary and secondary objectives of the study as defined by protocol. Additional analyses may be performed but are not covered by the current analysis plan.

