4.1. Patient accounting

Details of subjects screened, those who meet the study inclusion criteria, those who are eligible and enrolled, those who are eligible but not enrolled, those who withdraw from the study after randomization and those who are lost to follow-up will be summarized in a CONSORT flow diagram. The number of participants attending each annual survey will be reported. Since people were informed about their assigned study arm before providing consent and enrollment, the proportion of eligible subjects who are not enrolled will also be summarized by study arm.

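### Should the primary analysis have a pre-planned companion model adjusted for each village's first-survey leprosy burden?

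*SAP*

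**What the plan says.** SAP Section 7 fits a Poisson mixed model, specified as one "with incident case (0/1) as dependent variable, study arm as explanatory variable, using the non-intervention group (arm 1) as baseline level", with log time at risk as offset and nested random effects for island, block and village. Each of the three rate ratios against arm 1 is tested at p < 0.017. No baseline covariate and no adjusted companion model is named.

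Burden enters through the design. Section 2.1 states: "On the Comoros villages have been randomized after having been grouped by island into 'Blocks' of four in decreasing order of incidence". Reliable incidence figures were lacking for the Madagascar district, and the SAP gives this as the ground for a later allocation there: "randomization for Madagascar is foreseen only for the end of the first study year, once the first screening round has been completed".

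First-survey data exist for every arm: "In all four study arms, annual door-to-door surveys will be conducted covering entire villages". Section 5.1 limits their use, since "for Madagascar only data from the second survey onwards will be used for the primary objective", and then adds: "For secondary objectives 2 and 3 data from the first survey will also be used".

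Section 4.2 describes participants by arm, overall and by island. It has the clinical importance of any imbalance noted and rules out significance tests of it. Section 1 closes with "Additional analyses may be performed but are not covered by the current analysis plan".

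**The concern.** Blocks of four match villages only roughly, so villages in one block can still differ in burden. A whole-village survey at the start measures that burden and should predict later cases, yet the model does not use it. With only 16 to 18 villages per arm, variation between villages limits the precision of each rate ratio.

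There is also a question of discipline. If the report notes an imbalance and someone then wants an adjusted estimate, the SAP has no model ready. Its form would be chosen after results are known, and two comparative interim analyses make that more likely. The stakes would be wider intervals than necessary and an adjusted analysis open to the charge of selection.

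**Working it through.** **1. Number of villages.** Section 7 gives 8 blocks on Anjouan, 4 on Mohéli and 4 to 6 on Madagascar: 8 + 4 + 4 = 16 to 8 + 4 + 6 = 18. With four villages per block there are 64 to 72 villages, and 16 to 18 per arm.

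**2. Is the comparison fair without the covariate?** Within a block the four villages are allocated at random, one to each arm. Each village is equally likely to fall in any arm, so the expected difference in burden between arms is zero. Chance differences remain, and the village random effect is there to put them into the confidence interval. Leaving the covariate out can therefore cost precision but does not bias the comparison.

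**3. What precision could be gained?** The SAP gives no incidence, prevalence, between-village variance or correlation, so there is no figure of its own to reproduce. All four are assumed below.

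*Simple formula.* Take K blocks, m events per village, s the within-block SD of the village log rate, and r the within-block correlation of burden with the later log rate:

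Var(log IRR) = (2/K) × [1/m + s²(1 − r²)]

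For K = 16, m = 10, s = 0.5:
- arm only: (2/16) × (0.10 + 0.25) = 0.0438, SE 0.209
- adjusted, r = 0.5: (2/16) × (0.10 + 0.25 × 0.75) = 0.0359, SE 0.190

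That is an 18% lower variance. Over K = 16 to 18, m = 3 to 10 and s = 0.3 to 0.8, the reduction is 0% at r = 0, 2–8% at 0.3, 5–22% at 0.5 and 10–42% at 0.7. The formula treats burden as measured without error, which flatters the covariate. If the roughly 102,000 people screened (Section 3) are the trial villages, 102,000/68 = 1,500 live in each. At an assumed prevalence of 1.5 per 1,000 that is 2.25 first-survey cases per village, with a counting error on the log scale of about 1/√2.25 = 0.67. At 4 per 1,000 it is 6 cases and 1/√6 = 0.41. Such errors are as large as plausible true differences between villages.

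*Simulation with that noise included.* Assumptions:
- 8 + 4 + 5 blocks of four villages, 1,500 residents each, no true effect
- follow-up of 3 years on the Comoros and 2 in Madagascar; Comoros blocks ranked on five years of historic counts
- low rates per 1,000: incidence 1, prevalence 1.5, historic 0.5; high rates: 2, 4, 1
- village SD on the log scale 0.4, 0.6 or 0.9
- the Poisson mixed model with and without log((cases + 0.5)/screened); 800 trials per setting

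Variance of the log IRR, adjusted divided by arm-only:

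| Correlation | Madagascar blocked on first survey | Madagascar blocks unrelated to burden |
|---|---|---|
| 0.2 | 1.00–1.02 | 0.99–1.01 |
| 0.5 | 0.96–1.00 | 0.91–1.01 |
| 0.8 | 0.94–1.01 | 0.80–0.94 |
| 0.95 | 0.82–0.97 | 0.77–0.97 (one extreme setting, 0.62, set aside) |

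The Monte Carlo 95% half-width is 0.01 to 0.06. Interval width scales with the square root: √0.94 = 0.97, about 3% narrower; √0.80 = 0.89, about 11% narrower. Section 2.1 points to the left column, because Madagascar randomisation waits for the first screening round precisely for want of incidence data. It does not say so outright.

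**4. What would the covariate cost?** On the Comoros, allocation rested on 2013–2017 incidence and came before the first survey. Section 4.1 adds: "Since people were informed about their assigned study arm before providing consent and enrollment". The covariate would thus be measured after randomisation, with arm known, in 12 of 16 to 18 blocks (67% to 75%). If first-survey case detection in the Comoros PEP arms were 0.9, 1.1 or 1.2 times that of arm 1, the adjusted IRR in the simulation became 1.02–1.05, 0.97–0.98 or 0.95–0.97 times the arm-only IRR. The SAP does not show that this occurred. The adjusted Wald test also rejected slightly more often under no effect: 0.030 against 0.025 at nominal 0.017, and higher in 38 of 48 settings.

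**The case for a change.** The best case for an adjusted model is that it is cheap and closes off a later choice. In Madagascar the first survey precedes randomisation, so the covariate is clean there. Any case missed at the first survey and found later counts as incident, which strengthens the link between burden and outcome. With 0–40% of first-survey cases missed by village (mean 20%), first-survey blocking and correlations of 0.5 and 0.8, the ratios were 0.89 to 0.99, so at best √0.89 = 0.94, about 6% narrower. A second, smaller simulation (300 trials in each of four settings) gave 0.92, 0.97 and 0.93 with first-survey blocking. It gave 0.71 with arbitrary Madagascar blocks, high rates, SD 0.9 and correlation 0.8.

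It stands that no adjusted model is planned, and that adjustment might gain something in favourable settings. Three things take away its force.

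- If the arm-only model remains the deciding one, a narrower interval in a companion model alters no decision.
- As a robustness check it would be hard to read: on the Comoros, a gap between the two rate ratios could reflect chance imbalance or case-finding that differed by arm. Reported 2013–2017 incidence is free of that problem, but the Comoros blocks already rank on it.
- The post hoc worry is partly met. Section 1 places additional analyses outside the plan and requires major changes of method to be described and justified in the report. Section 4.2 creates no route from a noted imbalance to a changed model, and does not mention village burden.

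**Conclusion.** The concern does not hold. The SAP states nothing wrongly here and contradicts nothing. An arm-only model that follows the blocked randomisation and carries a village random effect is a standard choice. Keeping Madagascar's first survey out of the primary objective fits with randomisation there coming after it.

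The precision forgone rests wholly on assumed inputs. In the main simulation, with first-survey blocking in Madagascar and correlations up to 0.8, it runs from none to about 6% of the variance. It reaches about 20% only if Madagascar blocks are unrelated to burden, for which Section 2.1 gives no support. Against it stand a covariate measured after allocation in most blocks and a slightly higher false rejection rate. Statisticians may reasonably differ on whether to add such a model.

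This conclusion concerns the missing covariate only. It does not vouch for other parts of Section 7, such as the start of time at risk in each arm, nor for the exact size of the Wald test, which was above nominal in the simulation with or without the covariate.
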